Summary:	This study is an open-label, baseline-controlled, single-center study to measure the change in skin elasticity after combined radio frequency (RF) and pulsed electromagnetic field (PEMF) treatment. Forty-five adult females will undergo weekly treatments over a period of 8 weeks. Skin elasticity will be measured by a Cutometer® prior to beginning treatment, week 7 and 3 months after completion of treatment. Photographs will be taken prior to treatment, at week 4, week 7 and 3 months after completion of treatment. Patient discomfort/pain and satisfaction questionnaires will be completed before, during and after treatment.
Objectives:	The objective is to determine the quantitative change in elasticity of facial skin in subjects who have undergone treatment with combined RF and PEMF.
Endpoint	
Primary endpoint:
 
Quantitatively and objectively measure the change in facial skin elasticity following combined radio frequency and electromagnetic treatment. 
Secondary endpoints:
 
Improvement in facial skin laxity at 7 and 20 weeks post-intervention compared to baseline as assessed by blinded evaluators by photographic assessment utilizing the Fitzpatrick Wrinkle and Elastosis Scale (FWES) scale.Improvement in subject appearance at 7 and 20 weeks post-intervention compared to baseline as assessed by the subject utilizing the Global Aesthetic Improvement Scale (GAIS)Improvement in subject satisfaction with facial skin laxity at 4, 7 and 20 weeks post-intervention compared to baseline as measured by the 5-point Likert Subject Satisfaction questionnaire.
Population:	The study will enroll approximately 45 healthy adult females desiring improvement in facial skin elasticity and tightness.
Phase:	Post-approval
Number of Sites enrolling participants:	One site
Description of Study Agent:	Venus Versa is an FDA approved aesthetic device. The Diamondpolar applicator combining multi-polar RF and PEMF energies will be used in this study. It is approved for non-invasive skin tightening of the face in skin types I - IV.
Study Duration:	8 months

Participant Duration: 5 months

SCHEMATIC OF STUDY DESIGN

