3 OBJECTIVES AND PURPOSE

Primary objective:

Quantitatively and objectively measure the change in facial skin elasticity following combined radio frequency and electromagnetic treatment.

Secondary objectives:

Improvement in skin laxity at 20 weeks post-intervention compared to baseline as assessed by blinded evaluators by photographic assessment utilizing the Fitzpatrick Wrinkle and Elastosis Scale (FWES) scale.

Improvement in subject appearance at 7 and 20 weeks post-intervention compared to baseline as assessed by the subject utilizing the Global Aesthetic Improvement Scale (GAIS).

Improvement in subject satisfaction with skin laxity at 4, 7 and 20 weeks post-intervention compared to baseline as measured by the 5-point Likert Subject Satisfaction questionnaire.

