4.2.2 SECONDARY ENDPOINTS

Secondary endpoint #1: Change in photographic appearance of rhytids, as determined by blinded Facial Plastic & Reconstructive surgeons using the Fitzpatrick Wrinkle and Elastosis Scale (FWES) from baseline to week 20. Photographs from weeks 4 and 7 will only be used to track treatment progress, and will not be used by the raters to determine treatment efficacy.

Secondary endpoint #2: To assess clinical efficacy subjectively, the subjects will complete the Global Aesthetic Improvement Scale (GAIS), which is a 7-grade instrument.

Secondary endpoint #3: To assess satisfaction with the treatment, subjects will complete a 5-point Likert Subject Satisfaction scale.

The secondary endpoints serve to augment the findings of the primary endpoint. They help to provide a more complete understanding of treatment efficacy by including evaluations by trained physicians as well as the subjects themselves.

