5.4.2 HANDLING OF PARTICIPANT WITHDRAWALS OR TERMINATION

Every effort will be made to continue follow-up of withdrawn or terminated subjects or subjects who discontinue the intervention but remain in the study for follow-up, especially for safety and efficacy study endpoints. Every effort will be made to undertake protocol-specified safety follow-up procedures to capture AEs, serious adverse events (SAEs), and unanticipated problems (UPs). Subjects that withdraw will be replaced until a maximum of 60 subjects are randomized with 45 subjects expected to complete the study. Subjects that withdraw or are terminated from the study will still be requested to complete the week 20 follow-up procedure in order to evaluate for possible AEs or unanticipated problems (UPs).

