7 STUDY PROCEDURES AND SCHEDULE

7.1 STUDY PROCEDURES/EVALUATIONS

7.1.1 STUDY SPECIFIC PROCEDURES

- Medical history: obtained through interview. History will include age, other medical conditions, and previous invasive or non-invasive cosmetic procedure to the face or neck in the last 6 months.
- Medication history: current medications will be obtained through interview and will include prescription, over the counter, and herbal medications taken 4 weeks prior to study enrollment.
- Physical examination: completed by PI. Focused head and neck skin assessment that will include Fitzpatrick skin type and evidence of scars, infection, or inflammation of the face or neck.
- Imaging assessment: standard photos of the treated area will be taken by the PI using a Nikon D3100 using a 105 mm lens with fixed 2 Nikon flashes using diffuse bounce flash technique that reduces shadows and accentuates the subject's contours.
- Cutometer assessment at baseline, week 7 and at week 20.
- Rater assessment: The FWES will be used to rate the level of skin aging.
- Patient-reported outcomes: subjects will be asked to complete the GAIS questionnaire at weeks 7 and 20, and a 5-point Likert subject satisfaction scale at weeks 4, 7 and 20.

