7.3.2 ENROLLMENT/BASELINE

Enrollment/Baseline Visit (Visit 1, Week 0)

Once a subject has been confirmed that they continue to meet inclusion/exclusion criteria, each subject will receive a unique identifying number that will be composed of a two-digit site number and a three-digit subject number in sequence. This unique identifier will be used throughout the entire study and will be entered in the subject's CRF for each treatment.

Baseline Cutometer® measurements of the area to be treated will be obtained.

Subjects will be asked to refrain from using skin products or medications containing ingredients listed in the exclusion criteria, and may have to undergo washout periods for any such substances or medications prior to receiving treatment as part of this study. The Investigator should review the subject's skin care regimen and suggest appropriate alternatives for the course of the study, as needed.

All subjects will have photographs taken of the area to be treated. All subjects will be asked to remove all jewelry and piercings and wash the area to be photographed with provided cleanser to remove all makeup and skincare products. Subject will then wait 10 minutes for any washing related erythema to subside prior to initiation of photography session. All stray hairs will then be pulled away from the face. If seated photos, the stool height will be adjusted to ensure the subject's head, neck and spine are aligned and the subject is sitting up straight. Subject will then be positioned so they are centered in the frame using chin and forehead rests as applicable for seated three-point photo capture and if standing, feet are aligned with standardized photo foot marking on the floor standing straight with back flat against the draped back drop (blue, green or white) wall. All photography is to take place within the same room with standardized lighting, no natural light, for the duration of the study.

Standardized photographs will be taken using a high quality digital SLR camera to obtain three photos (frontal 90°, right 45° and left 45°). These photographs will be used as an assessment tool. They may also be used for publication and/or presentation of the study findings and generalized characterization of the disease state. Moreover, they may use the photographs for marketing or other commercial purposes.

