10.2 STATISTICAL HYPOTHESES

Statistical null hypothesis for primary endpoint: there will be no statistical change in gross elasticity as measured by the Cutometer[®] after treatment with combined RF/PEMF compared to before treatment.

Statistical null hypothesis for secondary endpoint #1: there will be no statistical change in the FWES as rated by blinded clinicians after treatment with combined RF/PEMF compared to before treatment.

Statistical null hypothesis for secondary endpoint #2: there will be no statistical change in the GAIS as rated by the subjects after treatment with combined RF/PEMF compared to before treatment.

Statistical null hypothesis for secondary endpoint #3: there will be no statistical change in the subject satisfaction score after treatment with combined RF/PEMF compared to before treatment.

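### Satisfaction is to be compared with baseline, but no satisfaction score is collected before treatment

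*Combined protocol and SAP*

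**What the plan says.** Three places set satisfaction against its pre-treatment level. Null hypothesis #3 in section 10.2 reads "there will be no statistical change in the subject satisfaction score after treatment with combined RF/PEMF compared to before treatment". The synopsis lists as a secondary endpoint "Improvement in subject satisfaction with facial skin laxity at 4, 7 and 20 weeks post-intervention compared to baseline", and section 3 has "Improvement in subject satisfaction with skin laxity at 4, 7 and 20 weeks post-intervention compared to baseline". The synopsis summary adds: "Patient discomfort/pain and satisfaction questionnaires will be completed before, during and after treatment".

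The operative sections schedule something narrower. Section 7.1.1 asks for "a 5-point Likert subject satisfaction scale at weeks 4, 7 and 20". The visit text in 7.3.3 and 7.3.4 places the form at Visits 5, 8 and 9, and the schedule in 7.3.7 marks the same three visits, with the screening and baseline cells empty. At baseline, section 7.3.2 requires Cutometer readings and states that "All subjects will have photographs taken of the area to be treated", but it mentions no satisfaction form.

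The endpoint definition in 4.2.2 describes the scale differently: "To assess satisfaction with the treatment, subjects will complete a 5-point Likert Subject Satisfaction scale". On analysis, section 10.4.3 says only that the score is a repeated measure.

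**The concern.** A change from before treatment needs a score from before treatment, or an instrument that itself asks about change. The plan schedules no such score, and nothing printed shows that the form is of the second kind. A repeated-measures model on the scheduled data can compare Weeks 4, 7 and 20 with one another, but that does not test null #3.

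The object being rated also shifts: skin laxity in the synopsis and section 3, the treatment in 4.2.2. A woman can rate her satisfaction with her skin before treatment, but not her satisfaction with a treatment she has not had. Adding a baseline form without settling this would not repair the endpoint.

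Timing matters because a prospective baseline score cannot be collected once treatment has begun. Section 10.1 finalises the analysis plan after data collection is complete, which is too late to add it.

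**Working it through.** The plan gives no sample size, power or effect figure for this endpoint, so there is no stated number to reproduce. The check compares the contrasts the plan states with the times at which the scale is collected.

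| Section | Satisfaction scale |
|---|---|
| Synopsis, section 3 | Weeks 4, 7 and 20, each against baseline |
| 10.2, null #3 | After treatment against before treatment |
| 7.1.1 | Collected at Weeks 4, 7 and 20 |
| 7.3.2 (Visit 1, Week 0) | Not collected |
| 7.3.3 (Visits 5 and 8) | Collected at Weeks 4 and 7 |
| 7.3.4 (Visit 9) | Collected at Week 20 |
| 7.3.7 | Marked at Weeks 4, 7 and 20; baseline empty |

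1. **Contrasts.** Three are stated: Week 4 against 0, Week 7 against 0, and Week 20 against 0. Each is computable only if both times are in the collection set. That set is {4, 7, 20}, Week 0 is absent, and so **0 of 3** are computable. With a Week 0 score the set is {0, 4, 7, 20} and **3 of 3** are computable.

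2. **Week 4 as a stand-in baseline.** Treatments are given at Weeks 0 to 7, eight in all. The Visit 5 text lists the Likert form ahead of that visit's treatment, so the treatments at Weeks 0, 1, 2 and 3 come before the first rating: 4 of 8. Any change in satisfaction over the first half of treatment would be missed.

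3. **Forms.** In 45 completers the schedule yields 45 × 3 = 135 satisfaction forms, none from before treatment. One more form at Visit 1 gives 45 × 4 = 180, which is 45 more. If all 60 subjects allowed by 5.4.2 are enrolled, 60 more baseline forms are needed.

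4. **GAIS for comparison.** Null #2 is also written as a change from before treatment, and GAIS is collected only at Weeks 7 and 20. But section 10.4.3 gives GAIS a signed range from -3 to 3, and the instrument rates improvement. Each GAIS score is therefore already a comparison with baseline: the null is badly worded, but no data are lost. Section 10.4.3 gives no such range or anchor for the satisfaction scale.

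**The case against.** The strongest reply is that this is a wording error. The plan uses the same baseline wording for GAIS, which needs no baseline form, and 4.2.2 defines endpoint #3 as satisfaction with the treatment, which fits a scale given only after treatment starts. On that reading the synopsis, section 3 and null #3 are the outliers. This is possible, and it is why the conclusion is conditional on the unprinted form. The text does not settle it, however. Nothing printed shows a change-anchored form, and the synopsis statement that questionnaires are also completed before treatment suggests that a baseline score was intended. Even on this reading, null #3 has to be rewritten.

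Other replies stand in part:

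- The scores could be compared with a neutral category. That is feasible, but it is a different hypothesis.
- A retrospective baseline rating could be sought later. It would be weaker because of recall bias.
- Women enrol because they want treatment for laxity, so low initial satisfaction is plausible. Section 5.1 sets no satisfaction threshold, so no baseline value can be assumed.
- The consequence is limited. This holds: 4.2.2 gives the secondary endpoints a supporting role, and the sample size in 10.5 does not rest on satisfaction.

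**Conclusion.** The concern holds. As written, the plan cannot test null #3 or report improvement in satisfaction from baseline: 0 of 3 stated contrasts are computable, and one of three secondary hypotheses is affected. The mismatch between the stated hypothesis and the collection schedule is certain from the text. The loss of information rests on one assumption, that the unprinted form does not itself rate change from baseline. If it does, only the wording is at fault.

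The scores at Weeks 4, 7 and 20 can still be described. The matter should be fixed before enrolment, but it is confined to one secondary endpoint. The GAIS null needs rewording only.

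**What to change.** First print the wording and anchors of the Likert form. If it already rates change from baseline, restate null #3 as no shift from the form's no-change anchor. Otherwise choose one option before enrolment.

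**Option A (preferred).** Add the item, worded as satisfaction with facial skin laxity, at Visit 1 before the first treatment, in 7.1.1, 7.3.2 and 7.3.7. Align 4.2.2 with that wording. In 10.4.3 name the contrasts (Weeks 4, 7 and 20, each against baseline), a method for paired ordinal scores, and the week that leads, since 10.4.9 makes no provision for multiplicity. The cost is one short form at an existing visit: 45 more forms, or up to 60 given that "Subjects that withdraw will be replaced until a maximum of 60 subjects are randomized with 45 subjects expected to complete the study". Satisfaction with the treatment is then no longer measured unless it is kept as a separate post-treatment item. A rise in an open-label study without a control group will still be hard to interpret.

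**Option B.** Remove null #3. In the synopsis and section 3, replace the baseline claim with the distribution of the score at Weeks 4, 7 and 20, with confidence intervals. Use one construct wording in the synopsis, section 3 and 4.2.2, and state in 10.4.3 that no contrast with baseline is made. Correct the synopsis sentence on questionnaire timing for pain as well as satisfaction, because the pain VAS is scheduled only after each treatment. The cost is wording only, but the claim of improved satisfaction is given up.

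Under either option, restate null #2 as no shift from the GAIS no-change value. This is wording only.

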10.3 ANALYSIS DATASETS

There will be one analysis dataset, which will only include subjects who completed the entire treatment and follow up protocol.

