10.4 DESCRIPTION OF STATISTICAL METHODS

10.4.1 GENERAL APPROACH

After data set compilation and cleaning, a series of descriptive statistics will first be generated to examine the data set for distributional/potential missing data patterns and sample characteristics. The study team will conduct a series of pooled time series analyses with generalized estimating equations regression (GEE) models.³ These types of non-parametric (i.e., not based on normal distribution assumptions) predictive modeling procedures are capable of using both robust and standard estimating functions to more fully evaluate the influence RF/PEMF treatments and other factors/covariates on serial face gross elasticity measurements. These types of procedures will also enable the study team to examine the potential effects of both *within group* (e.g., face gross elasticity measurements for Patient X at three measurement points) and *between group* (e.g., face gross elasticity measurement changes of younger women versus older women) model variables. A *P*-value of <0.05 will be considered statistically significant.

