10.4.2 ANALYSIS OF THE PRIMARY EFFICACY ENDPOINT(S)

Gross elasticity as measured by the Cutometer® is a ratio expressed as a percentage. Baseline and post-treatment measurements will be taken and analyzed using analysis of variance (ANOVA).

Results will be reported as baseline means with standard deviation, post-treatment means with standard deviation, and individual change for each subject.

Subjects with missing data, non-adherence, or lost to follow-up will not be included in the final analysis dataset.

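### Efficacy is analysed in protocol completers only, readings sought from withdrawn subjects go unused, and no sensitivity analysis is described

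*Combined protocol and SAP*

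**What the plan says.** Section 10.3 sets the population: "There will be one analysis dataset, which will only include subjects who completed the entire treatment and follow up protocol". Section 10.4.2 repeats the restriction for the primary endpoint: "Subjects with missing data, non-adherence, or lost to follow-up will not be included in the final analysis dataset". Neither section says how many treatments count as completion or what non-adherence means.

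Other sections seek outcome data from people this rule removes. Section 5.4.2 asks for continued follow-up of subjects who withdraw or stop treatment, "especially for safety and efficacy study endpoints". It also asks them to attend at week 20, giving adverse-event evaluation as the reason. Section 7.3.5 invites early terminators to complete Visit 9, which under 7.3.4 includes Cutometer readings, photographs, GAIS and satisfaction. A subject who leaves after Visit 8 also has a week 7 reading.

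On numbers, the protocol summary says: "The study will enroll approximately 45 healthy adult females desiring improvement in facial skin elasticity and tightness". Section 5.4.2 says: "Subjects that withdraw will be replaced until a maximum of 60 subjects are randomized with 45 subjects expected to complete the study".

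Section 10.4.1 plans descriptive statistics "to examine the data set for distributional/potential missing data patterns and sample characteristics" and then "pooled time series analyses with generalized estimating equations regression (GEE) models". Section 10.4.5, on adherence and retention, is marked not applicable. Section 10.4.10 lists individual data by time point. Section 10.1 says that an initial SAP exists and will be finalised after data collection.

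**The concern.** Completing the course is something that happens after baseline, and it may be related to how the skin responds, how painful treatment is or how satisfied the subject feels. The trial has one arm and compares each subject with her own baseline. If completers differ from the rest in their change, that difference is added to the estimated effect, and there is no control arm in which the same selection would show.

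Two features make this worse than ordinary attrition. First, the loss is partly self-inflicted: the protocol tries to obtain Visit 9 readings from withdrawn subjects, and the analysis rule then sets them aside. Second, the exclusion for non-adherence is undefined while the SAP stays open until data collection is complete. In an open-label study, the rule could therefore be settled when outcomes are already known.

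Replacing withdrawn subjects protects the number of completers. It does not protect against selection, and it does not cover subjects excluded for non-adherence alone.

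**Working it through.** **1. Share excluded.** From 5.4.2: 60 entered and 45 completing gives (60 − 45)/60 = 25%. From the protocol summary: 45 entered and all completing gives 0%. An intermediate case, 45 of 50, gives 10%. The 25% comes from a replacement maximum and an expected number of completers. It is neither a forecast nor a strict ceiling.

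**2. Possible bias in the completer mean.** Assumptions: no true change; individual change is standard normal; a latent tendency to complete has correlation r with change; those with the highest tendency are retained; one-sample t-test, two-sided 0.05. The documents give no value for r, so a range is shown.

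Large-sample formula: bias = r × φ(z)/q, where q is the share retained and z is the normal quantile that cuts off that share.

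- q = 0.75: φ(0.674)/0.75 = 0.318/0.75 = 0.424; at r = 0.3 the bias is 0.127 SD.
- q = 0.90: φ(1.282)/0.90 = 0.1755/0.90 = 0.195; at r = 0.3 the bias is 0.0585 SD.

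Simulation at the actual sample sizes (40,000 trials per cell), bias in SD / rejection rate:

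| Assumed r | 45 of 60 (25% out) | 45 of 50 (10% out) |
|---|---|---|
| 0 | 0.000 / 5.1% | 0.001 / 5.2% |
| 0.1 | 0.043 / 5.7% | 0.019 / 5.1% |
| 0.2 | 0.083 / 8.8% | 0.039 / 5.7% |
| 0.3 | 0.124 / 13.6% | 0.056 / 6.9% |

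To judge r: the bias equals the share excluded times the gap in mean change between completers and excluded subjects. At 25% excluded and r = 0.3 the gap is 0.127/0.25 = 0.51 SD, which is large.

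**3. What using the collected readings would do (25% excluded, r = 0.3).** If a random 0 / 4 / 8 / 15 of the 15 withdrawn subjects return inside the Visit 9 window and are analysed, the bias is 0.124 / 0.083 / 0.050 / 0.000 SD and rejection is 13.5 / 9.0 / 6.6 / 5.0%.

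If none returns, a missing-at-random model can use only week 7 readings. Assume a week 7 to Visit 9 correlation of 0.7 and dropout that depends on the Visit 9 change. With 15 / 8 / 4 / 0 of the 15 having a week 7 reading, the residual bias is 0.065 / 0.089 / 0.106 / 0.125 SD. The model does nothing for subjects with no post-baseline reading, so a sensitivity analysis is also needed.

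**4. Literal reading of completion.** Assume each of Visits 2 to 9 is missed independently with probability 2%.

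- Missed treatments not made up: excluded = 1 − 0.98^8 = 14.9%, or 6.7 of 45. Excluded with all three Cutometer readings = 0.98^2 × (1 − 0.98^6) = 11.0%, or 4.9 of 45.
- Missed treatments made up: only a missed Visit 9 excludes, so 2%, and none of those has all three readings.

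Sections 7.3.3 and 7.3.4 time Visits 3 to 9 from the preceding treatment, so making up a treatment is possible. The plan does not say which case applies.

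**5. Timing of an early Visit 9.** Section 7.3.4 places it 12 ± 2 weeks from the last treatment, that is 10 to 14 weeks. Section 5.4.2 says week 20, and 7.3.5 gives no time. By nominal weeks, week 20 is 13 weeks after a last treatment at week 7, 14 after week 6, 15 after week 5 and 17 after week 3. The two timings agree only if treatment stopped at week 6 or 7.

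**The case against.** The bias rests entirely on an assumed correlation. Nothing in the documents links change in R2 to completion, and R2 is read by an instrument, so selection may act on it less than on GAIS or satisfaction. A material distortion needs both high attrition and a high correlation. At r = 0.1 with 25% excluded, rejection is about 6%, and with 10% excluded even r = 0.3 gives about 7%. All of this stands. It limits what can be said about size, but not the fact that the plan has no way to detect a shift.

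A completer estimate is also defensible, because 2.1 and 2.2 ask whether the Cutometer can show improvement after treatment. That stands too, as a reason to keep the completer analysis. It does not justify having no other.

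Three stronger readings are tempting:

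- A reader might infer that 10.4.1 contradicts 10.3, since GEE can use incomplete records and missing-data patterns are to be examined. The examination could come before the final dataset is formed, and 10.4.1 justifies GEE on other grounds. The texts can be reconciled.
- A reader might infer that one missed treatment certainly removes a fully measured subject. That depends on whether missed treatments are made up, which is not stated.
- A reader might infer that no sensitivity analysis will ever be done. Because 10.1 leaves the SAP open, the documents support only that none is described in them.

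**Conclusion.** The concern holds, and the plan should be changed. The only efficacy dataset is defined by a post-baseline event, one of its exclusion terms is undefined, and readings sought from withdrawn subjects would not enter the efficacy analysis. The documents describe no all-treated analysis, no comparison of excluded with completing subjects and no sensitivity analysis.

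Confidence is high on these textual facts and low on magnitude. Under the stated assumptions the bias ranges from nil to about 0.12 SD, with rejection of 5 to 14% at 25% excluded, and reaches at most about 0.06 SD and 7% at 10% excluded. If everyone completes, there is none. A reader might infer that the result will be biased toward benefit, or that the false-positive rate is 14%. The documents support neither: a shift toward benefit is plausible, but its direction and size are unknown, and 14% is the worst of the cases tabulated. Safety is less affected, because 10.4.4 reports all adverse events.

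**What to change.** - **10.3:** define the primary efficacy set as all subjects with a baseline Cutometer reading and at least one treatment, regardless of adherence, using all available week 7 and Visit 9 readings. Keep completers as a supportive set, and define completion and non-adherence for it before data are seen.
- **10.4.2:** delete the exclusion sentence. Analyse R2 at baseline, week 7 and week 20 as three nominal time points in one longitudinal model valid under missing at random (a mixed model, or GEE with weights or multiple imputation).
- **Early-termination readings:** count one as week 20 only if it falls inside the stated Visit 9 window. List other exit readings with their dates, outside the model. Sections 5.4.2, 7.3.4 and 7.3.5 must be reconciled on when this visit falls.
- **Sensitivity analysis:** give subjects without a Visit 9 reading no change, then progressively worse values until the conclusion changes.
- **10.4.5:** replace the not-applicable entry with counts, reasons for exclusion, and baseline R2 for excluded versus completing subjects.

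Cost: wording changes, one model, one sensitivity run and a short table. No visits or measurements are added, because Visit 9 is already requested from withdrawn subjects. The downside is a little more analysis work and a possibly less favourable estimate, which describes starting the course; the supportive completer analysis still describes finishing it.

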5.4 PARTICIPANT WITHDRAWAL OR TERMINATION

5.4.1 REASONS FOR WITHDRAWAL OR TERMINATION

Subjects are free to withdraw from participation in the study without prejudice at any time upon request. In the event that a subject drops out of the study or is withdrawn from the study, the Exit/Termination CRF form should be completed. On the withdrawal page, the Investigator should record the date of the withdrawal, the person who initiated withdrawal and the reason for withdrawal.

Reasonable effort will be made to contact any subject lost to follow up during the course of the study in order to complete assessments and retrieve any outstanding data and study medication/supplies. The records of subjects who terminate prior to completing the study will be retained and the reason for termination will be documented.

An investigator may terminate participation in the study if:

- Any clinical adverse event (AE), laboratory abnormality, or other medical condition or situation occurs such that continued participation in the study would not be in the best interest of the participant.
- The subject meets an exclusion criterion (either newly developed or not previously recognized) that precludes further study participation.

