7.3.5 EARLY TERMINATION VISIT

Subjects who terminate the study early for whatever reason, will be asked to return to the clinic, if they are willing, to complete the final visit (Visit 9). Adverse events and the reason for early termination will be recorded.

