10.4.4 SAFETY ANALYSES

There are no formal safety endpoints in this study, however all AEs and relevant information related to the incidents (start date, stop date, severity, relationship, outcome, and duration) will be recorded and reported. Adverse events leading to premature discontinuation from the study and serious treatment emergent AEs will be presented in a table.

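### The single completer-only dataset (10.3) conflicts with the promised table of AEs leading to discontinuation (10.4.4), and no safety population is defined

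*Combined protocol and SAP*

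**What the plan says.** Section 10.3 defines one population for the whole study: "There will be one analysis dataset, which will only include subjects who completed the entire treatment and follow up protocol". Section 10.4.2, under the primary efficacy endpoint, adds: "Subjects with missing data, non-adherence, or lost to follow-up will not be included in the final analysis dataset".

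Section 10.4.4 says there are no formal safety endpoints but commits to recording and reporting "all AEs and relevant information related to the incidents". It then specifies one tabulation: "Adverse events leading to premature discontinuation from the study and serious treatment emergent AEs will be presented in a table". It names no population or denominator.

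Three other parts of the plan bear on who stops and what is known about them:

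- **Stopping can be caused by safety.** Section 5.4.1 lists among the grounds for termination: "Any clinical adverse event (AE), laboratory abnormality, or other medical condition or situation occurs such that continued participation".
- **Women who withdraw are replaced.** Section 5.4.2: "Subjects that withdraw will be replaced until a maximum of 60 subjects are randomized with 45 subjects expected to complete the study".
- **Their AE data are sought.** Section 5.4.2: "Subjects that withdraw or are terminated from the study will still be requested to complete the week 20 follow-up procedure". Section 7.3.5, on early termination: "Adverse events and the reason for early termination will be recorded".

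Section 10.4.5 marks adherence and retention analyses as not applicable, so no other planned analysis accounts for the women who stopped.

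**The concern.** A table of AEs that ended participation describes women who did not finish. A dataset restricted to women who did finish cannot supply it. Because an AE is itself a ground for termination, membership of the completer set can depend on the safety outcome, and replacement would then fill the vacated place with another woman.

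The gap is wider than one table. Section 8.1 names the pain VAS and the examination of the treated area as the safety parameters, and 7.3.7 schedules both at all eight treatment visits. Neither has an assigned analysis population. Under 10.1 the SAP is finalised only after data collection is complete. In an open-label study that leaves the safety denominator to be settled when the AEs are already known.

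Repairing the efficacy population would not necessarily close this gap. A set requiring a post-baseline Cutometer reading, for example, would still omit a woman who stopped after one treatment and never returned for a reading.

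**Working it through.** The plan states no AE rate or safety denominator, so there is no figure to reproduce. The check is a comparison of definitions, followed by a count.

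**Step 1. Definitions side by side.**

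- Set A (10.3): women who completed all treatment and all follow-up.
- Set B (10.4.4, discontinuation table): women who left the study early because of an AE.

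Taking early discontinuation to mean not completing the protocol, A and B share no members. A table of B drawn from A has zero entries regardless of what happens. One borderline case is undefined: a woman recorded as withdrawn after her eighth treatment who still attends Visit 9. It does not change the general result.

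**Step 2. Women who could fall outside set A.** The inputs are the cap of 60 and the 45 expected completers, both from 5.4.2. That section speaks of randomised subjects; in this single-arm study I read that as enrolled.

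- 60 − 45 = 15
- 15 / 60 = 25%

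This assumes that the cap is reached and that all 15 received at least one treatment. If, say, 5 of the 15 left before treatment, the all-treated set would be 55 and the share left out 10 / 55 = 18.2%. If the 10.4.2 exclusions also removed women who attended to the end, the number would rise; the documents give no figure for that.

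**Step 3. What the choice of set does to the discontinuation table.** Let x be the number of women who stop because of an AE. The documents give no rate, so x is an assumption and is shown across its range. Completers contribute no such events by definition. Intervals are exact (Clopper-Pearson): lower limit = Beta quantile 0.025 with parameters (x, n − x + 1); upper limit = Beta quantile 0.975 with parameters (x + 1, n − x); n = 60.

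| x (assumed) | Completer set | All treated | 95% CI, all treated |
|---|---|---|---|
| 1 | 0/45 | 1/60 = 1.7% | 0.04–8.9% |
| 3 | 0/45 | 3/60 = 5.0% | 1.0–13.9% |
| 5 | 0/45 | 5/60 = 8.3% | 2.8–18.4% |
| 15 | 0/45 | 15/60 = 25% | 14.7–37.9% |

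For 0/45 the two-sided 95% upper limit is 1 − 0.025^(1/45) = 7.9%. That limit carries no information about the women left out: the second column is the same in every row.

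**The case against.** The strongest reply is that 10.3 was meant for efficacy only. It follows directly on 10.2, whose four hypotheses all concern efficacy, and the matching exclusion rule sits under the primary efficacy endpoint in 10.4.2. Section 10.4.4 speaks of all AEs, and its promise of a discontinuation table itself shows an intention to report on women who stopped.

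Collection and escalation are also well covered. Sections 5.4.2 and 7.3.5 seek AE information after withdrawal, 8.3 requires every on-study AE to be documented, 8.4.2 sends every SAE to the sponsor within 24 hours, and 10.4.10 lists individual data. A burn that caused a withdrawal would be unlikely to go unrecorded.

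Much of this stands. A reader might infer that the plan will report no discontinuation AEs, or that its AE rates will be biased downward. The documents do not support either inference: 10.4.4 never says its tables use the completer set, and it plans no AE rates. Nor is there any sign of an intention to hide events.

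What the reply does not supply is a population. Section 10.3 is worded for the whole study, not for efficacy, and none of the sections cited names a safety set or denominator.

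**Conclusion.** The point holds as a conflict between two stated rules, together with a missing definition. Read literally, 10.3 makes the table promised in 10.4.4 impossible to fill, and nothing elsewhere resolves it.

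The size is conditional. Only if safety summaries were built on the one defined dataset would the discontinuation table be empty and up to 15 of 60 women (25%) be left out. The 25% rests on the replacement cap being reached and on every withdrawal following a first treatment; it is not a forecast of dropout. The rates tabulated for different values of x are illustrations, not estimates.

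This should be fixed, preferably before the AE data are known. It is not a fatal flaw: the study is post-approval, its objective is elasticity, and AE data are to be sought from the women concerned.

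**What to change.** 1. In 10.3, state that the completer dataset applies to efficacy analyses only. Whether completers are the right efficacy population is a separate question.
2. In 10.3, add a safety set: every subject who received at least one RF/PEMF treatment.
3. In 10.4.4, state that all AE, local tolerability (immediate-response) and pain VAS summaries use the safety set as their denominator.

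A short disposition summary with reasons for stopping would make the discontinuation table easier to read; 5.4.1 already requires those reasons to be recorded.

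The cost is about two sentences of protocol and SAP wording. No new data, visits or procedures are needed, and clinical management is unchanged. The one downside for the sponsor is that AE figures may look slightly less favourable than they would among completers alone.
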